## **9. RESEARCH METHODS**

### **9.1 STUDY DESIGN**

A multi-centre, open-label, prospective, real-world non-interventional study over a 6 month period of patients with COPD prescribed re-usable Respimat® SMI, will be conducted.

It will include two patient cohorts: (1) Respimat SMI-experienced, defined as patients who have been on maintenance treatment with a Respimat SMI product (Spiriva®, Striverdi® or Spiolto®) and receive a refill prescription at study entry and (2) Respimat SMI-naïve, defined as patients who have not previously used a Respimat SMI product and receive their first prescription at study entry. The prescription at study entry for both cohorts should be for a re-usable Respimat SMI product.

[figure not shown]
The Respimat SMI-experienced patient cohort will further be divided into two subgroups: (1a) patients on maintenance treatment with a re-usable Respimat SMI at study entry; and (1b) patients on maintenance treatment with a disposable Respimat and switching to a re-usable Respimat SMI at study entry ([Figure 1](#)).

Patients will be followed from the time of study entry (enrolment visit) for a period of approximately 4-6 weeks (study period) ([Figure 1](#)). The minimum pack size for the re-usable Respimat SMI is 30 days (4 weeks), after which the follow-up assessment will be conducted. An additional 2 week follow-up window has been included to account for scheduling of clinic visits and/or provision of time for the patient to complete the PASAPQ and the questions on the ease of handling of the re-usable Respimat SMI.

The primary outcome is satisfaction with the re-usable Respimat SMI attributes in patients with COPD, which will be measured by the PASAPQ total score (from 13 questions) at the end of the study period (follow-up assessment, [Figure 1](#)) for all patients.

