**Exclusion criteria:**

Patients fulfilling any of the following exclusion criteria will not be eligible for participation in the study:

- Patient using a disposable Respimat SMI product during the study period, after study entry
- Patient who have had a severe COPD exacerbation requiring hospitalisation in the immediate 3 months prior to study entry
- Patient participating in a clinical trial or any other non-interventional study of a drug or inhaler at the time of enrolment
- Visual, cognitive, motor or health impairment that, as judged by the investigator, may cause concern regarding the patient's ability to complete the questionnaires
- Patient not fluent and literate in one of the main languages of the country

Where allowed by local regulations, a patient screening log will be kept at each site, recording basic information such as age at COPD diagnosis, gender, information on the eligibility (or reasons for non-eligibility/non-enrolment, including a reason for refusal [if known]). In addition, a log of all patients included into the study (i.e. having provided informed consent) will be maintained in the Investigator Site File irrespective of whether they have completed the study or not.

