### **9.3 VARIABLES**

This is a non-interventional study design enrolling consented patients with COPD who will be treated with a re-usable Respimat product (Spiriva, Striverdi or Spiolto), according to their approved summary of product characteristics. Patients will be enrolled consecutively and will be followed over a period of approximately 4-6 weeks ([Figure 1](#)). Data, as listed in [Table 1](#), will be collected, where available.

Table 1: Visit flow chart and data variables to be collected

	Study entry (Baseline)	Follow-up assessment (4-6 weeks after baseline)
Informed Consent	X	
Inclusion / Exclusion Criteria	X	
Patient demographics (e.g. age, gender, height, weight)	X	
Duration of COPD	X	
CAT or mMRC score (if available)	X	
Pulmonary function (based on most recent spirometry test in the 12 months prior to study entry  ) (if available)	X	
Disease severity based on 2019 GOLD grade and group 	X	
Respimat® SMI product prescribed (Spiriva®, Striverdi® or Spiolto®)	X	
Duration of treatment with disposable Respimat SMI 	X	
Last day of use of disposable Respimat SMI 	X	
Date of first prescription of re-usable Respimat SMI	X	
Number of COPD exacerbations (in the 12 months prior to study entry) and during the study period	X	X
COPD-related and other concomitant medications (in the 6 months prior to study entry and during the study period  )	X	X
Comorbidities	X	X
Smoking status / history	X	X
PASAPQ completed by the patient 	X	X
Respimat SMI type used during study period (disposable or re-usable)		X
Questions on the ease of handling of re-usable Respimat SMI		X
Question on Respimat SMI preference (disposable vs re-usable) 		X
Safety: Serious and non-serious ADRs, AEs with a fatal outcome and other reportable safety events		X
Details of discontinuation of the re-usable Respimat SMI during the study period  (if applicable)		X

 If more than one measurement is available in the 12-month period prior to study entry, the measurement closest to the study entry will be included.

 GOLD grade (1-4) and patient group (A, B, C or D) will be appraised based on available exacerbation history, assessment of symptoms based on CAT, and GOLD spirometry classification of airflow limitation based on post-bronchodilator spirometry results, if available (GOLD 2019).

 This will be assessed in Respimat SMI-experienced patients only.

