#### **9.4.1.1 Validation of receipt of re-usable Respimat SMI Question**

The re-usable Respimat SMI can be differentiated from the disposable Respimat SMI through the position of the dose indicator. In the re-usable Respimat SMI the dose indicator is attached to the base of the cartridge and in the disposable Respimat SMI, the dose indicator is located on the side of the inhaler. Patients will be advised to contact the sites if they are not dispensed a re-usable Respimat SMI product at study entry.

Additionally, at the time of the follow-up visit, single question will be asked to all patients to confirm the re-usable version of Respimat SMI was being used during the study period (Table 2).

Table 2: Validation of receipt of re-usable Respimat SMI

Validation of receipt of re-usable Respimat SMI		Scoring
Type of inhaler	What type of inhaler have you been using since commencing the study?	- Re-usable inhaler - Disposable inhaler

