#### **9.4.2 Patient Reported Outcome (PRO) assessment**

##### **9.4.2.1 Patient Satisfaction and Preference Questionnaire (PASAPQ)**

The patients' satisfaction with regard to the handling of the re-usable Respimat SMI will be measured by the self-administered, 15-item PASAPQ that includes a performance domain (7 items), a convenience domain (6 items), an overall satisfaction question (Item 14) and a question on willingness to continue with inhaler (Item 15). Only the questions in the performance and convenience domains count towards the total score. Questions 1-14 are answered using a 7-point ordinal scale with divisions from very dissatisfied to very satisfied; question 15 is answered using a value from 0-100, with zero indicating that the patient would not be willing to continue using the inhaler and 100 indicating that the patient would definitely be willing to continue using the inhaler ([Kozma et al. 2005](#)). The PASAPQ has been translated and validated for use in all the main languages of the study countries.

To calculate the total score, the sum of the 13 items of the two domains (performance and convenience; items 1-13) are transformed to a 0- (least) to 100- (most) point scale, with higher scores indicating greater satisfaction. Missing data in the PASAPQ is handled as follows ([Miravittles et al. 2016](#)):

- If half or more than half of the questions in the individual domains (performance and convenience) of the PASAPQ are missing for a patient, no score is calculated and the PASAPQ domain score is marked as missing.
- If a patient answers at least half of the questions in the domain, values for missing questions will be imputed using the mean of the remaining, non-missing questions in that domain.

The PASAPQ will be administered to all patients (Respimat SMI-experienced and Respimat SMI-naïve) at the follow-up assessment. Additionally, for the Respimat SMI-experienced

patients switching from a disposable to a re-usable Respimat SMI product at study entry, PASAPQ will be administered at the baseline visit (see [Figure 2](#)).

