The PASAPQ will be administered in electronic format, with the provision for administration in paper format, if required. The electronic questionnaire will be designed using a mobile-first approach. The patients will receive a link to the PASAPQ via email, which they can complete using their hand-held electronic devices (such as smartphone, iPad or tablet), laptop or desktop computer. The link will be provided as follows:

- At baseline visit (study entry): to the Respimat SMI-experienced patients switching from a disposable to a re-usable Respimat SMI product at study entry – the link will be valid for up to 3 days after the baseline visit.
- At study end (i.e. 4 weeks after the baseline visit): to all patients (Respimat SMI-experienced and Respimat SMI-naïve) – the link be valid for up to 2 weeks after study end.

Patients unable to complete the PASAPQ electronically may be provided with a paper version of the PASAPQ at study enrolment (baseline visit), if applicable. It can also be mailed (with a pre-paid return envelope) to patients to be completed up to 2 weeks after study completion (follow-up assessment).

Table 3: PASAPQ questions and scoring

	Domain	Question	Scoring
Total Score	Performance	Q1: Overall feeling of inhaling your medicine	Items scored on a 7-point Likert scale: 1 = Very dissatisfied 2 = Dissatisfied 3 = Somewhat dissatisfied 4 = Neither satisfied nor dissatisfied 5 = Somewhat satisfied 6 = Satisfied 7 = Very satisfied
		Q2: Inhaled dose goes to lungs	
		Q3: Amount of medication left	
		Q4: Works reliably	
		Q5: Ease of inhaling a dose	
		Q10: Using the inhaler	
		Q11: Speed medicine comes out	
	Convenience	Q6: Instructions for use	
		Q7: Size of inhaler	
		Q8: Durability of inhaler	
		Q9: Ease of cleaning inhaler	
		Q12: Ease of holding during use	
		Q13: Convenience of carrying	
	Overall	Q14: Overall satisfaction with the inhaler	

	Domain	Question	Scoring
	satisfaction question		
	Question on willingness to continue with inhaler	Q15: Willingness to continue using the inhaler that was used during the study	Score ranges from 0-100, with 0 indicating that the patient would not be willing to continue using this inhaler and 100 indicating that the patient would definitely be willing to continue

	Study enrolment (baseline)	Follow-up assessment (study end)

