## **ANNEX 3. PATIENT SATISFACTION AND PREFERENCE QUESTIONNAIRE (PASAPQ) DIRECT VERSION**

### **PART 1: RATING OF SATISFACTION WITH INHALER ATTRIBUTES**

**Instructions:** For the following questions, please check the response that best describes how satisfied you are with each of the following items. Please take as much time as you need to answer each question.

		Very Dissatisfied	Dissatisfied	Somewhat Dissatisfied	Neither Satisfied nor Dissatisfied	Somewhat Satisfied	Satisfied	Very Satisfied	
How satisfied are you...									
1.	With the overall feeling of inhaling your medicine?	Inhaler							
2.	With the feeling that the inhaled dose goes to your lungs?	Inhaler							
3.	That you can tell the amount of medication left in your inhaler?	Inhaler							
4.	That the inhaler works reliably?	Inhaler							
5.	With the ease of inhaling a dose from the inhaler?	Inhaler							
6.	With the instructions for use?	Inhaler							
7.	With the size of your inhaler?	Inhaler							
8.	That the inhaler is durable (hard wearing)?	Inhaler							

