**Please go to the next page**

		Very Dissatisfied	Dissatisfied	Somewhat Dissatisfied	Neither Satisfied nor Dissatisfied	Somewhat Satisfied	Satisfied	Very Satisfied
9.	With the ease of cleaning your inhaler?							
10.	With using the inhaler?							
11.	With the speed at which medicine comes out of the inhaler?							
12.	With the ease of holding the inhaler during use?							
13.	With the overall convenience of carrying the inhaler with you?							
14.	Overall, how satisfied are you with your inhaler?							

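### Some switchers' baseline PASAPQ forms may rate the re-usable inhaler, because the form can be answered after the switch, its satisfaction items do not name the device, and the SAP change score checks neither

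*Protocol*

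**What the plan says.** Protocol 9.1 defines subgroup 1b as "patients on maintenance treatment with a disposable Respimat and switching to a re-usable Respimat SMI at study entry". The exclusion criteria in Protocol 9.2.3 list "Patient using a disposable Respimat SMI product during the study period, after study entry", and a footnote to Table 1 starts the study period at the baseline visit. Protocol 9.4.1.1 expects the new device to be dispensed at entry: "Patients will be advised to contact the sites if they are not dispensed a re-usable Respimat SMI product at study entry".

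For this subgroup, Protocol 9.4.2.1 says that "PASAPQ will be administered at the baseline visit". It then says of the emailed link that "the link will be valid for up to 3 days after the baseline visit". Patients who cannot use the link may be given a paper form at enrolment, with no baseline deadline stated.

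The Annex 3 items are generic, for example "With the size of your inhaler" (item 7) and "Overall, how satisfied are you with your inhaler" (item 14). Item 15, which does not enter the total or domain scores, refers to the inhaler used in the study, and at baseline that does not point to the disposable.

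SAP 8.4 equates baseline with the enrolment visit. SAP 20.2.1.4 takes follow-up minus baseline in the FAS for the total, performance and convenience scores, with no rule on when the baseline form was answered or which device it rates.

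**The concern.** The paired change can be read as disposable versus re-usable only if the first form rates the disposable. A form answered one to three days after the visit falls in a period when the plan itself expects the patient to be using the re-usable inhaler. A patient asked then about the inhaler in general terms may rate the new one. The pair would compare the re-usable inhaler with itself at two times, yet enter the analysis as a device comparison.

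This is bias, so enrolling more switchers does not remove it. It concerns the only comparison for which the plan gives a power calculation. The plan does ask about device identity, but only at follow-up (Protocol 9.4.1.1, SAP 19) and for the period since entry. The baseline half of the pair has no equivalent question.

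**Working it through.** **1. The plan's own figure.** Inputs from Protocol 9.5 and SAP 6: paired t-test, two-sided alpha 0.05, difference 8 points, SD of differences 18, n=56. Power comes from the noncentral t distribution with n-1 degrees of freedom and noncentrality (d/SD) x sqrt(n) = (8/18) x sqrt(56) = 3.33. The result is 90.4%, which agrees with the stated 90%. Allowing for 10% non-evaluable patients, 56/0.9 = 62.2, rounded up to 63, as stated.

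**2. What contamination would do.** The documents give neither quantity needed, so both are assumptions:
- c = share of baseline forms that rate the re-usable inhaler;
- e = early re-usable rating minus disposable rating, in points.

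Affected pairs show a mean change of 8 - e and clean pairs show 8. The expected observed change is (1 - c) x 8 + c x (8 - e) = 8 - c x e.

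At c = 10% (about 6 of 56 forms), with the SD kept at 18:

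| e | Meaning | Observed change | Power, n=56 | Power, n=97 |
|---|---|---|---|---|
| 12 | first impression better than follow-up | 6.8 | 79% | 96% |
| 8 | early rating equals follow-up | 7.2 | 84% | 97% |
| 4 | halfway | 7.6 | 87% | 98% |
| 0 | early rating equals the disposable rating | 8.0 | 90% | 99% |
| -4 | first impression worse than the disposable | 8.4 | 93% | 99.5% |

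(n=97 is the plan's scenario for 6 points at 90% power.)

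At c = 5% and n=56, e = 8 gives a change of 7.6 (87%), e = 4 gives 7.8 (89%) and e = -4 gives 8.2 (92%).

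**3. Effect of the mixture on the SD.** For c = 10% and e = 8, the mixture SD is sqrt(18^2 + 0.1 x 0.9 x 8^2) = 18.16. Power at n=56 is then 83.0% instead of 83.7%, which changes nothing of substance.

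**4. Where it would start to matter for power.** At n=56, 80% power needs a difference of 6.86 points. Power drops below 80% when c x e exceeds 8 - 6.86 = 1.14, that is c above 1.14/8 = 14% (e = 8) or 1.14/4 = 29% (e = 4). At n=97 the needed difference is 5.17, so c must exceed 2.83/8 = 35% (e = 8).

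**5. Can the planned data separate the forms?** In part.
- "Last day of use of disposable Respimat SMI" is scheduled at study entry only (Protocol Table 1). If it is completely missing, it is set to the consent date (SAP Appendix 2).
- SAP 19 counts use of the new device from the prescribed date. No first-use date for a switcher's new inhaler is named.
- SAP 19 and Appendix 2 do refer to a dispensed date. A form completed before it can be taken as clean, provided the completion date is stored, which the documents do not say.
- For a form completed after dispensing, no planned variable shows which device was rated.

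No such check is written into SAP 20.2.1.4.

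**The case against.** The strongest reply is that three things must coincide in one patient: the form is answered after the visit, the new inhaler has been dispensed and used by then, and the patient rates it instead of the long-used one. None of these has a documented frequency. The form is planned for the visit, three days is only the outer limit of the link, entry is defined by a prescription, and dispensing may come later. Annex 3 is a generic version of the questionnaire. The electronic screens, the link email and the patient instructions are not in the documents and may name the device. All of this stands, and it makes the point a risk and not a shown error.

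The size argument also stands. At c = 10% and e = 8 the bias is 0.8 points, against a 95% CI half-width of about 4.8 points at n=56 (2.004 x 18/sqrt(56)) and a quoted minimum important difference of 8-10 points. SAP 9.1 calls every test exploratory.

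A reader might infer that the planned data cannot sort the forms at all. The documents do not support that, because the dispensed date could clear some of them. A reader might also take the fall to 84% as a worst case. It is not: a first impression better than the later rating lowers the observed change further.

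What remains is that nothing in the two documents stops a re-usable rating from being analysed as a disposable baseline, and that exploratory status does not make such a pair interpretable.

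**Conclusion.** The point holds as a possible bias in the before-after change in total, performance and convenience scores for switchers. The affected share and the direction are unknown: towards zero if early ratings of the new inhaler resemble the later ones, absent if they equal the disposable rating, away from zero if first impressions are worse. Under the assumed shares of 5-10% and an early rating no better than the follow-up rating, the observed change would lie between 7.2 and 8.4 points for e from -4 to 8, and power at n=56 between 84% and 93%.

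A reader might go further and conclude that objective 3 is invalid, or that the study's main result is in doubt. Neither follows. Most forms may well be answered at the visit. The primary outcome uses only the study-end form, and the preference question names both devices. The case for acting rests on the low cost of the remedy and on this being the one powered comparison, not on the illustrated loss of power. Priority: low to moderate.

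**What to change.** **Protocol 9.4.2.1.** Have switchers complete the baseline PASAPQ, electronic or paper, at the baseline visit where possible and otherwise before first use of the re-usable inhaler, without delaying treatment. Keep the 3-day link as a fallback so that baseline forms are not lost.

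**Baseline form.** Outside the validated items, add one instruction line: *Please rate the disposable Respimat you have been using up to now.* Record the completion date. If the form is being changed anyway, add one yes/no item on whether the new inhaler has already been used.

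**SAP 20.2.1.4.** Keep all FAS baseline forms in the main paired analyses of the three scores. Add one sensitivity analysis limited to forms completed on the visit day, completed before the dispensed date, or answered *No* to the new item, and report the counts in each group. Call it supportive: once the instruction line is in place it may drop valid ratings of the disposable, and it selects early responders. Do not classify forms by the imputed last-use date.

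**Cost.** A small protocol and eCRF change, one line (and possibly one item) translated for the participating countries, and one extra analysis. The validated wording, the FAS and the main analysis are unchanged. If 50 of 56 forms qualify, the sensitivity analysis has 87% power for 8 points. The SAP is dated October 2019 and gives September 2019 for the start of enrolment, so patients enrolled before the change would be covered only by the date-based check, if their completion dates were stored.

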## **4. ABSTRACT**

Name of company: Boehringer Ingelheim			
Name of finished medicinal product: Re-usable (1) Spiriva® Respimat® 2.5 microgram inhalation solution; (2) Striverdi® Respimat® 2.5 microgram inhalation solution; and (3) Spiolto® Respimat® 2.5 microgram / 2.5 microgram inhalation solution			
Name of active ingredient: (1) Tiotropium; (2) olodaterol; and (3) tiotropium/olodaterol			
Protocol date: 11 Jun 2019	Study number: 1237-0097	Version/Revision: 1.0	Version/Revision date: N/A
Title of study:	A real-world non-interventional study to assess patient satisfaction with and preference for re-usable Respimat Soft Mist inhaler in patients with chronic obstructive pulmonary disease.		
Rationale and background:	
Inhaled medications are the mainstay of pharmacological treatment (both rescue therapy and maintenance treatment) for patients with chronic obstructive pulmonary disease (COPD). A number of inhaler devices are available, and their selection is based on patients' needs and preferences, depending on device characteristics and patient capabilities.
 
The Respimat® Soft Mist™ inhaler (SMI) (Spiriva®, Striverdi® or Spiolto®) has been available since 2004 for the delivery of treatments to patients with COPD or asthma and has gained widespread use. While Respimat SMI was initially available as a 'disposable' inhaler that patients were only able to use for the labelled number of doses following insertion of the cartridge, feedback from patients and physicians resulted in modification of the disposable Respimat SMI to become an environmentally friendly re-usable inhaler.
 
Studies have shown that greater treatment satisfaction is associated with improved adherence and persistence with medication; critical to improving health outcomes for patients. Therefore, as part of the post-marketing evaluation of the re-usable Respimat SMI, it is important to assess patients' satisfaction and preference for the re-usable features of the device in the real-world setting.
		

Name of company: Boehringer Ingelheim			
Name of finished medicinal product: Re-usable (1) Spiriva® Respimat® 2.5 microgram inhalation solution; (2) Striverdi® Respimat® 2.5 microgram inhalation solution; and (3) Spiolto® Respimat® 2.5 microgram / 2.5 microgram inhalation solution			
Name of active ingredient: (1) Tiotropium; (2) olodaterol; and (3) tiotropium/olodaterol			

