#### **9.2.4      Study visits / assessments**

Patients will have two assessments: one at study enrolment (baseline visit) corresponding to their routine clinic visits for treatment of COPD, and one at end of the study period (follow-up assessment), which will occur approximately 4-6 weeks after the baseline visit. The follow-up assessment can be completed during the routine clinic visit or remotely (by telephone) if the patient does not visit the site (clinic) within 4-6 weeks of the baseline visit. No additional clinic visits or assessments are mandated or recommended for this study.

All patients will have the PASAPQ administered at study end (follow-up assessment). The PASAPQ will be administered in electronic format, with the provision for administration in paper format, if required. For the Respimat SMI-experienced patients switching from a disposable to a re-usable Respimat SMI product at study entry, the PASAPQ will be administered twice: (1) at study enrolment (baseline visit); and (2) at study end (follow-up assessment).

The pack size for the re-usable Respimat will cover 30 days (1 month), or 90 days (3 months), depending on the country. It is therefore anticipated that patients prescribed larger pack sizes may not return to the clinic at the time of follow-up assessment. Therefore, the PASAPQ, as well as the questions on the ease of handling of the re-usable Respimat SMI and patient preference, will be administered either electronically or mailed to patients (depending on patient preference) to be completed offsite (remotely) (see [Section 9.4.2.1](#)).

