#### 9.4.2.2 Ease of handling questions

For all patients, the ease of handling of the re-usable Respimat SMI will be completed at the time of follow-up assessment, using a set of individual questions with answers to each question scored on a 7-point ordinal scale, with divisions from very dissatisfied to very satisfied (see [Table 4](#) for details).

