#### 9.4.2.3 Question on patient preference for re-usable or disposable in Respimat SMI-experienced patients

A single question will be asked only to the Respimat-experienced patients switching from a disposable to a re-usable Respimat SMI product at study entry, to determine their preference

for the type of Respimat SMI: re-usable vs the disposable Respimat SMI (see Table 4 for details).

Table 4: Ease of handling questions and patient preference (for Respimat SMI-experienced patients switching from disposable to re-usable Respimat SMI at the time of study entry)

For all patients		Scoring
Ease of handling	
Q1: How satisfied are you with the ease of removing the clear base?
 
Q2: How satisfied are you with the grip of the cartridge?
 
Q3: How satisfied are you with inserting a new cartridge?
 
Q4: How satisfied are you with the readability of the dose indicator?
 
Q5: How satisfied are you with recognising when you need to replace the cartridge?
 
Q6: How satisfied are you with automatic detachment of the clear base when the cartridge is empty?
 
Q7: How satisfied are you with automatic return to the start-use position when replacing the clear base?
 
Q8: How satisfied are you with the overall ease of handling the inhaler?
 
Q9: How satisfied are you with the sustainability (eco-friendly) concept of the inhaler, due to re-use ability?
 
Q10: How satisfied are you with recognising when to replace the inhaler?
	
All items scored on a 7-point Likert scale:
 
1 = Very dissatisfied          2 = Dissatisfied          3 = Somewhat dissatisfied          4 = Neither satisfied nor dissatisfied          5 = Somewhat satisfied          6 = Satisfied          7 = Very satisfied
 
1 = Very dissatisfied          2 = Dissatisfied          3 = Somewhat dissatisfied          4 = Neither satisfied nor dissatisfied          5 = Somewhat satisfied          6 = Satisfied          7 = Very satisfied          8 = Not applicable

Only for Respimat SMI-Experienced patients switching from disposable to re-usable Respimat SMI at the time of study entry		
Rating of inhaler preference	Q1: Comparing the re-usable with disposable inhaler, please indicate which inhaler do you prefer to use?	
 
- Re-usable inhaler
 
- Disposable inhaler
 
- No preference
 

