20.2.1.3 Re-usable Respimat® SMI Ease of Handling

Analysis Set: FAS

The secondary analysis to evaluate the ease of handling of re-usable Respimat® SMI used in the study will be performed overall and by patient cohort.

Ease of handling will be accessed using a set of individual items with answers ranging from 1 (very dissatisfied) to 7 (very satisfied) and will be collected from the “Ease of Handling (ePRO)” or “Ease of Handling (Paper)” eCRF pages.

The following ease of handling of re-usable Respimat® SMI items will be summarised using descriptive statistics for categorical variables:

- Q1: How satisfied are you with the ease of removing the clear base?
- Q2: How satisfied are you with the grip of the cartridge?
- Q3: How satisfied are you with inserting a new cartridge?
- Q4: How satisfied are you with the readability of the dose indicator?
- Q5: How satisfied are you with recognising when you need to replace the cartridge?
- Q6: How satisfied are you with automatic detachment of the clear base when the cartridge is empty?
- Q7: How satisfied are you with automatic return to the start-use position when replacing the clear base?
- Q8: How satisfied are you with the overall ease of handling the inhaler?
- Q9: How satisfied are you with the sustainability (eco-friendly) concept of the inhaler, due to re-use ability?

Document: \\ .net\Enterprise\Sites\USCBG\Depts\BioStat\Boehringer\Documentation\SAP\Final

Author: Version Number: 1.0
Version Date: 100CT2019

Template No.: RWI_TP_BIOS0013 Revision 1

Reference: RWI_WI_BIOS0015

Effective Date: 15Jun2018

- Q10: How satisfied are you with recognising when to replace the inhaler?

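### The study-end questions can open two days before a 30-day supply runs out, so some new users may rate cartridge-exchange items (ease-of-handling Q5–Q7) before any exchange, and the SAP does not separate them

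*Protocol*

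**What the plan says.** Protocol 9.1 (Study Design) ties the follow-up to the pack: "The minimum pack size for the re-usable Respimat SMI is 30 days (4 weeks), after which the follow-up assessment will be conducted". The Abstract makes the same equation. Section 9.4.2.1 provides the study-end PASAPQ link "At study end (i.e. 4 weeks after the baseline visit): to all patients", and keeps it open for a further 2 weeks.

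That sentence names only the PASAPQ. The shared timing of the other questions comes from two other places. Section 9.4.2.2 states: "For all patients, the ease of handling of the re-usable Respimat SMI will be completed at the time of follow-up assessment". Section 9.2.4 has the PASAPQ, the ease-of-handling questions and the preference question administered together, electronically or by mail. It also says: "The pack size for the re-usable Respimat will cover 30 days (1 month), or 90 days (3 months), depending on the country".

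Three of the ten ease-of-handling items in Table 4 turn on the end of a cartridge. One reads "Q6: How satisfied are you with automatic detachment of the clear base when the cartridge is empty". Q5 asks about knowing when the cartridge is due for a change. Q7 asks about the reset when the clear base goes back on. Table 4 also prints a second answer scale with an eighth, not-applicable code; the table as available does not show which items carry it.

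SAP 20.2.1.3 analyses ease of handling for all patients together and within each cohort. All ten items are tabulated as categorical variables on a scale of 1 to 7, with no condition on a cartridge having been changed. SAP Appendix 4 likewise lists only codes 1 to 7.

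**The concern.** The Abstract says that "it is important to assess patients' satisfaction and preference for the re-usable features of the device in the real-world setting". Cartridge exchange is one of those features. A naïve patient, or one switching from the disposable device (subgroup 1b), comes to the first exchange only when the first cartridge is finished. A patient who answers before then has nothing to base Q5–Q7 on, and must guess, choose a neutral rating or skip the item.

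Neither document asks whether an exchange has taken place. The breakdown by cohort does not help, because patients before and after their first exchange sit in the same cohort. The Q5–Q7 tables could therefore mix experienced and hypothetical ratings in unknown proportion, and a reader of the report could not separate them. Switchers give their preference at the same follow-up, so part of that result may also precede any re-use of the device.

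**Working it through.** **Inputs from the documents**
- Link opens 4 weeks after the visit and stays valid for 2 more weeks (Protocol 9.4.2.1).
- Minimum pack is 30 days (Protocol 9.1).
- 1 week = 7 days; 1 month = 30.4375 days (SAP Appendix 1).
- Dispensed and prescribed dates are separate dates (SAP Appendix 2), so first use can fall after the visit.

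**Assumption:** one cartridge lasts 30 days. The documents give pack duration, not cartridge life.

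**Step 1. The plan's own equation.** 4 × 7 = 28 days, and 30 / 7 = 4.29 weeks. Thirty days is not 4 weeks, and the one-month reading (30.4375 days) does not give 28 either. The stated equivalence does not reproduce.

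**Step 2. Earliest exchange against the window.** The window runs from day 28 to day 28 + 14 = 42. With first use on the visit day and no missed dose, the cartridge covers days 0 to 29, so an exchange is first needed on day 30. The link opens 30 − 28 = 2 days earlier.

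**Step 3. Share answering before the cartridge is empty, replies uniform over days 28–42.** Let L be the dispensing lag in days and a the adherence. Exhaustion day E = 30/a + L, and share = (E − 28)/14.

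| L | a | E | Share |
|---|---|---|---|
| 0 | 100% | 30 | 2/14 = 14% |
| 3 | 100% | 33 | 5/14 = 36% |
| 7 | 100% | 37 | 9/14 = 64% |
| 3 | 90% | 36.3 | 8.3/14 = 60% |

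Counting whole days instead (28 to 42 inclusive is 15 days), the first row is 2/15 = 13%.

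**Step 4. Prompt replies, no lag, full adherence.** With exponential reply times of mean m days, truncated at 14, share = (1 − e^(−2/m)) / (1 − e^(−14/m)). This gives 63% for m = 2, 49% for m = 3 and 35% for m = 5.

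Only the two-day gap comes from the documents, given the cartridge-life assumption. The lag, the adherence and the reply-time distribution are scenarios, because the documents give no data on any of them.

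**Step 5. Who and what is exposed.** Naïve and 1b patients have no earlier exchange; patients already on the re-usable device (1a) may have had one. Q6 depends on an empty cartridge by its own wording, and Q5 and Q7 by their natural reading. Q1–Q3 plausibly arise at first loading. Q4, Q8 and Q9 do not need an exchange.

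**The case against.** The best defence has four parts.

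*The window stays open to day 42.* Many patients will answer after an exchange, and the gap that needs no assumption about lag or reply time is only two days. This is right, and it limits the claim to some patients.

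*The protocol offers a not-applicable answer.* Where it applies, a patient without the experience has a valid response and can be identified. This could cover Q10 or the exchange items. But its scope cannot be seen, and the SAP neither lists the code nor says whether it enters the percentages. The defence therefore does not carry through to the analysis.

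*The affected items are secondary and descriptive.* This is correct. A reader might infer that the primary result is compromised because the link in question is the PASAPQ link. The documents do not support that: none of the 15 PASAPQ items asks about cartridge exchange.

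*Preference is an overall judgement.* A reader might also infer that the ease-of-handling and preference objectives fail as a whole. They do not. Protocol 7 lists simpler assembly, daily use and the dose indicator among the improvements, alongside cartridge exchange. A switcher can form a real preference from those, so that result is only partly affected.

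**Conclusion.** The point holds in a narrow form. The protocol's intention to assess after the 30-day pack is not met by a link that opens on day 28 from the visit. If a cartridge lasts 30 days, some naïve and switching patients can rate Q5–Q7 before their first exchange, and the SAP pools those ratings with experienced ones. With uniform replies, no dispensing lag and full adherence the share is about 14%. Lag, missed doses or early replies raise it by an amount that the documents cannot fix.

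Two stronger readings should be resisted. One is that most replies precede an exchange: that needs an assumed lag, adherence or reply pattern. The other is that Q10, on knowing when to replace the inhaler, cannot be answered by any new user. With up to 6 cartridges at 30 days each, 6 × 30 = 180 days lies far beyond day 42. But that rests on the same inferred cartridge life, and the not-applicable option may already serve Q10.

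**What to change.** 1. **Protocol 9.1 and Abstract:** correct the equation of 30 days with 4 weeks.
2. **Protocol 9.4.2.1 and 9.4.2.2:** open the ease-of-handling questions no earlier than day 30 and keep the close at day 42. This stays inside the existing 4–6-week follow-up and leaves 12 days to reply.
3. **Table 4:** add one yes/no item, *Have you replaced a cartridge in this inhaler?* It is needed even with a day-30 opening, because late dispensing or missed doses can still push the exchange later. If no item can be added, derive exchange status from the completion date against the dispensed date + 30 days. That is only an approximation: it assumes full adherence and needs both dates on record.
4. **SAP 20.2.1.3:** summarise Q5–Q7 among patients who have replaced a cartridge.
5. **SAP 20.2.1.5:** add a supportive table of preference by replaced yes/no.
6. **Table 4, SAP 20.2.1.3 and Appendix 4:** state which items carry the not-applicable code. List it in the SAP, report its count, and leave it out of the satisfaction percentages, notably for Q10 if it applies there.

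The cost is a short wording change in both documents, one extra item, and a smaller denominator for Q5–Q7. If the PASAPQ link stays at day 28, the ease-of-handling questions also need a separate release. Moving the whole study-end link well beyond day 30, for example to a fixed interval after dispensing, is not needed: it would shift the primary PASAPQ and could break the 4–6-week window for the sake of items outside the primary score.
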